9.1	OUTCOMES.....	25
9.2	SAMPLE SIZE	26
10	QUALITY CONTROL AND QUALITY ASSURANCE	26
11	ETHICS/PROTECTION OF HUMAN SUBJECTS.....	26
11.1	ETHICAL STANDARD	26
11.2	ETHICAL APPROVAL	27
11.3	INFORMED CONSENT	27
11.4	EXCLUSION OF WOMEN, MINORITIES, AND CHILDREN (SPECIAL POPULATIONS)	27
11.5	SUBJECT CONFIDENTIALITY.....	27
11.6	STUDY DISCONTINUATION	27

12	DATA HANDLING AND RECORD KEEPING	27
12.1	DATA COLLECTION	27
12.2	CASE REPORT FORMS (CRFs).....	27
12.3	DATA MANAGEMENT	28
12.4	STUDY RECORDS RETENTION.....	28
12.5	PROTOCOL DEVIATIONS AND VIOLATIONS	28
13	PUBLICATION POLICY	28
14	REFERENCES CITED.....	29
TABLE 1. LABORATORY SPECIMENS TO BE OBTAINED AT EACH VISIT OR BY SELF-COLLECTION		31
TABLE 2. TABLE OF STUDY PROCEDURES.....		33

PROTOCOL SUMMARY

Title:	Effects of a vaginal contraceptive ring on vaginal microbiota and local immunity
Population:	Premenopausal women 18 years of age or older with BV or recent history of BV, desire to use CVR, and not intending to become pregnant over the course of participation
Number of Sites:	1
Study Duration:	5 years
Participation Duration:	7 months (plus optional 6 month extension)
Description of Agent or Intervention:	Contraceptive vaginal ring (CVR)
Objectives:	To assess potential benefits associated with both intermittent (use for 3 weeks, remove for 1 week, as defined in the package insert) and continuous (use for 4 weeks, then replace) CVR use among women either with BV or at high risk for BV. We will also recruit women who are HSV2-infected.
Time to Complete Enrollment:	18 months

1 BACKGROUND INFORMATION

1.1 Significance

Our objective is to study effects of a contraceptive vaginal ring (CVR) containing estrogen and progesterone (NuvaRing) on vaginal bacteria (the vaginal microbiome), local immunity, and lower genital tract infection in women. Emerging data suggest a favorable effect of this CVR on vaginal bacteria, specifically hydrogen peroxide-producing lactobacilli (LB), which are supported when the vagina is under the influence of estrogen.^{1,2} These lactobacilli are critical for defense against infection with HIV and other sexually transmitted infections (STI). Bacterial vaginosis (BV) is characterized by loss of these LB and instead, overgrowth of a mix of anaerobic bacteria. BV significantly increases risk of STI/HIV, including genital herpes caused by HSV2.^{3,4} BV is characterized by declines in protective immunologic mediators (certain defensins, secretory leukocyte protease inhibitor (SLPI)) and increases in inflammatory cytokines and chemokines,⁵ alteration of cervical immune cell populations⁶ and activation of local immune cells, including T cells.⁷ Whether local delivery of hormones through a product like the CVR restores the lactobacilli and the protection they provide from BV and STI/HIV is unknown. In contrast, the contraceptive systemic depot progesterone—commonly used worldwide—may independently increase risk of HIV acquisition and transmission.⁸ Our overarching hypothesis is that NuvaRing contributes to reduction in BV, healthy markers of cervicovaginal immune response and decreased rates of HSV2 shedding. Long-acting vaginal delivery of hormonal contraception as the foundation of “multicomponent prevention” – for example, delivery systems that can combine activity against unintended pregnancy, HIV, and other STI—has become a major focus for scientists, advocates, and funders alike,⁹⁻¹¹ but effects on the vaginal environment need careful definition before broad implementation.

The need for contraceptive options has taken on urgency with evidence indicating that systemic hormonal contraception (primarily injectable, long-acting progestin) may increase women’s risk of HIV acquisition and transmission to male sex partners.¹² Lack of other contraceptive options is a critical barrier to progress towards optimizing women’s reproductive health. Moreover, BV remains a major problem for women, causing symptomatic vaginitis and conferring increased risk for adverse outcomes of pregnancy and STI/HIV acquisition. We propose to explore the hypothesis—supported by limited data—that a contraceptive vaginal ring (CVR) that is commonly used in the U.S., the NuvaRing, will enhance women’s genital and reproductive health. We propose that this CVR will increase the bacteria that help the vaginal environment protect against infection by HIV and other STIs, reduce rates of BV, and that in women who already have HSV2, use of the CVR will lower HSV2 shedding in the female genital tract. Importantly, CVR acceptability in general is excellent.¹³ Moreover, the format of drug delivery through the form of a vaginal ring is also being intensely explored with the use of antiretroviral agents (dapivirine, tenofovir) as a means of topical, female-controlled HIV prevention, and formulation work with several antiretroviral drugs for sustained delivery with the NuvaRing format is underway.⁹

We believe the NuvaRing specifically will enhance vaginal health because we hypothesize that it will promote the growth of the *Lactobacillus* bacteria that protect women from infection with HIV and other STI. These bacteria, called *L. crispatus* and *L. jensenii*, are promoted by adequate levels of vaginal estrogen. These bacteria maintain low vaginal pH (<4.7) by producing lactic acid. BV occurs when these vaginal lactobacilli are replaced by overgrowth of other vaginal bacteria (primarily anaerobes, or bacteria that live in low-oxygen conditions). BV is the most common cause of vaginal complaints in reproductive-aged women. In pregnant women, BV is strongly associated with increased risk of preterm births and pregnancy-associated infections. In non-pregnant women, BV increases the risk of pelvic

infections, and acquisition of multiple STI, including HSV2 and HIV.¹⁴ BV may elevate these risks in several ways, including activation of local immune cells. Finally, recent data indicate that onset of menstruation triggers key shifts in local vaginal bacteria, and in many women, may actually precipitate BV. Continuous use of the NuvaRing (use for four weeks, then replace) suppresses menstruation, and is increasingly used by many women with excellent reports of acceptability and safety. Whether this suppression of menstruation could suppress BV recurrence is not known.

Although short-term antibiotic therapy improves symptoms and restores *Lactobacillus* predominance in most women with BV, up to 20% of women fail routine therapy. In addition, BV recurrence after successful therapy is the rule. Recurrence is likely caused by failure to recolonize the vagina with desirable lactobacilli, which requires adequate vaginal estrogenization. In one study, women who used the NuvaRing for 3 consecutive 28-day cycles had higher quantities of desirable vaginal lactobacilli relative to women who used oral contraceptive pills containing 20 µg ethinyl estradiol and 100 µg levonorgestrel.¹ The NuvaRing releases 120 mcg/day of ENG (the active metabolite of desogestrel, a progesterone) and 15 mcg/day of ethinyl estradiol (the estrogen component). While generally well tolerated, incidence of local complaints (increased vaginal discharge or discomfort) with continuous CVR use is higher than those reported by OC users;¹⁵ thus, the risk: benefit ratio of this approach needs careful assessment.

Pregnancy is also an independent risk for HIV acquisition and transmission, when acquisition confers high rates of perinatal transmission.^{16,17} However, systemic depot progesterone, commonly used worldwide, may independently increase risk of HIV acquisition and transmission.⁸ Increased HIV risk related to hormonal contraceptive use would be of global public health importance, given the large number of women using such methods. In a recent technical report, the World Health Organization noted that “expansion of contraceptive method mix and further research on the relationship between hormonal contraception and HIV infection is essential.”¹⁸

For all of these reasons, then, a careful study of the microbiological, clinical, and immunologic benefits of the CVR is a high scientific and public health priority.

1.2 Study Hypothesis

- CVR use will be associated with favorable vaginal changes assessed by BVAB qPCR, and community definition by high-throughput sequencing
- Initiation of CVR use will be associated with an increase in desirable protective factors in the vagina, including increases in SLPI and reduction in proinflammatory cytokines.
- CVR use will be associated with lower rates of and longer time to incident BV assessed by clinical status (Amsel criteria and symptoms)¹⁹ and Nugent score,²⁰ and among HSV-2-infected women, with a reduction in HSV-2 shedding.

2 STUDY OBJECTIVES

We propose to assess potential benefits associated with both intermittent (use for 3 weeks, remove for 1 week, as defined in the package insert) and continuous (use for 4 weeks, then replace) CVR use

[figure not shown]
among women either with BV or at high risk for BV. We will also recruit women who are HSV2-infected.

Primary outcomes will be as follows:

- The primary outcomes will be the quantity of *L. crispatus* determined by species-specific qPCR assay (Aim 1), local immune parameters, including cytokines and innate mediators (Aim 2), and incidence of and time to clinical BV episodes over the course participation (with the exploratory aim of measuring genital HSV-2 shedding among HSV-2 seropositive women (Aim 3).
- Secondary objectives will include a determination of Nugent score on Gram stain of vaginal fluid, vaginal colonization with bacteria associated with BV, the vaginal microbiome as determined with broad range 16S rRNA and pyrosequencing, and rates of adverse events with CVR use. At study end, all participants will be offered the choice of continuing NuvaRing use, or will be counseled on alternative (non-CVR) contraception methods. Women who opt to switch to an intrauterine device (IUD) at the end of the study will be offered participation in IUD an Extension Study, in which we will follow subjects for an additional 6 months to assess changes in immunity and the microbiome after IUD placement.

[figure not shown]
3 STUDY DESIGN

Figure 1. Study Design & Timeline

¹At the Month 7 End of Study Visit, subjects who opt to have an IUD placed for contraception will be offered participation in optional IUD Extension Study.

Timeline for Optional Hormonal Sub-Study Participants

¹Subjects who are BV- at screening may enroll at the same visit.

²At the Month 6 visit, subjects are given the opportunity to discontinue CVR use.

4 STUDY ENROLLMENT

4.1 Eligibility Criteria

- Women who are 18 years of age or older
- BV+ by Amsel criteria and Nugent score OR history of BV in the prior 12 months
- Premenopausal (as defined by having had at least 3 menstrual periods in the last 6 months, unless using hormonal contraception in which the investigators will use clinical discretion in determining eligibility).
- Willing to stop hormonal contraception
- Willing to use the NuvaRing as directed
- Not intending or wishing to become pregnant over the course of the study
- Daily access to a freezer for specimen storage
- Capable of providing written informed consent

4.1.1 Additional Eligibility Criteria for Enrollment into Hormonal Sub-Study

- BV negative at Screening/Enrollment
- Have regular menstrual cycles 25-35 days in length
- Have not used hormonal contraception within the past 2 months (no DMPA within the past 6 months)

4.1.2 Additional Eligibility Criteria for Enrollment into Optional IUD Extension Study

- Completion of Month 7 End of Study Visit
- Desiring IUD placement
- Willing to have IUD placed at Public Health STD clinic or by other health care provider
- No contraindications to IUD use (current pelvic inflammatory disease, distorted uterine cavity due to fibroids or other uterine pathology)

4.2 Exclusion Criteria

- Current pregnancy
- Women who are less than 6 weeks postpartum
- Contraindications to hormonal contraceptive use per package insert, including history of deep vein thrombosis, smoking in women older than 35 years
- IUD at study initiation
- Unable to comprehend consent material because of language barrier or psychological difficulty

4.3 Withdrawal from Study

Subjects are free to withdraw from the study at any time. Subjects who become pregnant during the course of the study will not continue the study. If a subject withdraws from the study due to CVR side effects or other issues and has used the CVR for at least 2 cycles, we will ask that they complete one final month of daily home swab collection.

4.4 Study Termination

The study may be terminated at any time by the principal investigator.

5 STUDY INTERVENTIONS

5.1 Study Overview

This study will be conducted at the University of Washington Virology Research Clinic (VRC) located at Harborview Medical Center in Seattle. Eligible women with BV will be invited to enroll as will women with a high likelihood of experiencing BV in the near term (12 months). We plan to enroll approximately 120 women.

Among those with BV at Enrollment, all will be treated with standard antibiotic therapy. After assessment for cure at 7-10 days, they will be asked to return for a visit at one month from enrollment to establish their baseline status. They will be offered non-hormonal methods for pregnancy prevention during that initial month.²¹ After one month (Month 2 visit), they will then be asked to initiate NuvaRing use using one of the following two approaches:

- Continuous CVR use for four 28-day cycles, with replacement of the CVR after each cycle
- Non-continuous CVR use involving use for 21 days, then removal for 7 days, with replacement after the 7-day CVR-free period

Following initiation of CVR use, all participants will be evaluated monthly for BV with standard criteria (Amsel and Nugent criteria) and have specimens obtained for performance of bacterial quantitative PCR (qPCR) assays for BV-associated bacteria, *L. crispatus* and *L. jensenii*. Women will also be asked to seek care with the study team for interim vulvovaginal symptoms, with provision of diagnostic workup and appropriate treatment.

While participants will have the right to voluntarily stop using CVR at any point during the study, they will specifically be offered the option of discontinuing CVR use at six months (after 4 months of use) for the purpose of documenting whether the vaginal environment changes after CVR cessation. For this, they will return for one additional monthly visit.

5.1.1 Hormonal Sub-Study

In a sub-study of 40 women, we will compare cervicovaginal effects of the contraceptive ring to the normal changes occurring during the luteal phase of the menstrual cycle in response to endogenous estrogen and progesterone. Cervical cytobrush specimens will be collected to obtain an adequate sample of endocervical epithelial cells, which will be used for microarray-based gene expression analyses. Subjects who are otherwise eligible for the main study and who are BV negative, have regular menstrual cycles 25-35 days in length, and have had no use of hormonal contraception within the past 2 months (no DMPA within the past 6 months) will be eligible for the sub-study. Hormonal Sub-study participants will be asked to return for one additional visit prior to initiation of CVR for serum progesterone level testing and collection of cervical cytobrush samples in addition to regular visit specimens (same as Visit 1).

5.1.2 Intrauterine Device (IUD) Extension Study

During the Month 7 visit (or after completion of the study), we will offer women enrollment in an optional Extension Study, which aims to assess changes in cervicovaginal immunity, vaginal microbiome, and HSV-2 shedding among participants who opt to initiate an IUD. Subjects who have completed the Month 7 visit and daily vaginal swabs during the main study will be eligible to participate. All participants will receive counseling on contraceptive options at completion of the main study. Women who opt for an IUD will receive information regarding clinics that offer IUD placement, including the Public Health – Seattle & King County STD Clinic and other local family planning clinics. Subjects will receive IUD placement per standard of care at individual clinics; IUDs will not be placed as part of study procedures. IUD Extension Study participants will be asked to return approximately one month after IUD placement for their first Extension Study Visit. Women who previously participated in the Hormonal Sub-study will also have cytobrush specimens and progesterone levels collected at 2 time points during the IUD Extension Study.

5.2 Study samples

5.2.1 Vaginal Fluid

Swabs of vaginal fluid will be obtained from the posterior fornix for PCR assays. BV diagnosis will be made using any three of the following: (1) vaginal pH ≥ 4.7 , (2) clue cells $>20\%$ of vaginal epithelial cells on microscopy, (3) fishy odor with KOH and (4) abnormal vaginal discharge (increased amount, differing from usual consistency, or malodorous). Diagnostic evaluation for *C. trachomatis*, *N. gonorrhoeae*, and *Trichomonas vaginalis* will be performed using nucleic acid amplification testing (APTIMA-Combo, GenProbe).

Women with any condition for which treatment or further testing is indicated will be managed

according to standard guidelines, and will remain eligible for enrollment. BV will be treated with standard treatment (either metronidazole gel .75%, one application vaginally nightly for 5 days, or oral metronidazole, 500 mg orally twice daily for 7 days, according to the participant's preference). All women treated for BV will be asked to return at 7-10 days for a test-of-cure visit, with BV cure defined by absence of >2 Amsel criteria.

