5.3 Contraception

After the enrollment visit, women will be asked to maintain a one-month period of no hormonal contraceptive use. They will be counseled on non-hormonal methods of contraception (abstinence, barrier methods) and will be provided male and/or female condoms (as they prefer) at no cost.

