Aim 3. The primary outcomes will be (1) incidence of BV at all available follow-up visits, and (2) time to BV during four months of CVR use relative to the two months prior to CVR use. For secondary analysis, we will measure the quantity of HSV-2 by PCR. This will be log transformed and association with CVR use examined using a linear mixed model as for Aim 1. *Sample size calculation:* Data from our prospective studies of BV were used to estimate the likelihood of these conditions occurring during follow-up. Over six months of observation, we have documented BV recurrence rates after cure of an initial BV episode of 28 / 100 person-years in absence of any hormonal contraception. A recent meta-analysis estimated that HC was associated with a 30% reduced likelihood of BV.²⁵ With these assumptions, we will have reasonable power to detect a 30% or greater difference in incidence of BV by CVR status (Table 5). However, BV incidence may be lower, and mechanisms for a favorable shift in vaginal microbiome, if affected by CVR, may be heterogeneous. If so, we will still be able to generate important preliminary data in support of the CVR's favorable effect on the vaginal environment through demonstration of improved microbiome maintenance and immune profile; this would support future study of the CVR in populations with higher incidence of BV and other cervicovaginal STI.

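### Aim 3's BV outcome has no stated Nugent confirmation, so increased discharge, which may be ring-related, can decide whether a visit counts as BV

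*Combined protocol and SAP*

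**What the plan says.** **The outcome.** Section 2 gives the Aim 3 primary outcome as "incidence of and time to clinical BV episodes over the course participation" and lists the Nugent score separately, among the secondary objectives. Section 9.1 (Aim 3) restates it as "1) incidence of BV at all available follow-up visits, and (2) time to BV during four months of CVR use", compared "relative to the two months prior to CVR use". Neither section gives an event definition or asks for Nugent confirmation.

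**The diagnostic rule.** Section 5.2.1 states that "BV diagnosis will be made using any three of the following": raised pH, clue cells, amine odor with KOH, and "4) abnormal vaginal discharge (increased amount, differing from usual consistency, or malodorous". The features of the fourth sign are joined by *or*, so an increased amount is enough on its own. Section 7.1 has discharge characterized visually at the pelvic examination. No section says how discharge attributable to the ring is handled when this sign is scored.

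**The ring and discharge.** Section 1.1 says that "incidence of local complaints (increased vaginal discharge or discomfort) with continuous CVR use is higher than those reported by OC users".

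**Where Nugent appears.** The hypothesis on incident BV (Section 1.2) names Amsel criteria, symptoms and Nugent score. Section 5.1 uses both systems at the monthly evaluations. Section 7.2.1 describes the Gram stain as confirming BV, and Section 7.2.2 has it read without knowledge of clinical condition. Only the secondary BV outcome of Aim 1 (Section 9.1) is written as Amsel-defined and Nugent-confirmed.

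**The concern.** Aim 3 is an open-label comparison of ring months with the same women's earlier months. If one component of the outcome can respond to the ring itself, misclassification can differ between the two periods. Here the component is a visually judged sign, scored when ring status is known. A visit with two other signs is not BV without discharge and is BV with it.

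The bias would run against the trial's hypothesis: extra events in ring months would shrink or mask a true reduction. Few BV events are expected in either period, so a handful of such visits could change the conclusion. Section 5.1 also asks women to seek care for vulvovaginal symptoms between visits, so discharge could prompt additional BV assessments.

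**Working it through.** **1. Can discharge decide the diagnosis?** The other three signs (pH, clue cells, odor) have 2 × 2 × 2 = 8 patterns.

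| Other signs present | Patterns | BV without discharge | BV with discharge |
|---|---|---|---|
| 0 or 1 | 4 | no | no |
| 2 | 3 | no | **yes** |
| 3 | 1 | yes | yes |

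In 3 of the 8 patterns discharge alone changes the result. It never does so unless two other signs are present.

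**2. Inputs from the plan.** Section 9.2: 120 women, 75% analyzable, and 120 × 0.75 = 90, which reproduces the stated figure. Section 9.1, Aim 3: 28 per 100 person-years without hormonal contraception, a 30% reduction, four ring months and two months before.

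**3. Expected events in 90 women**
- Ring time: 90 × 4/12 = 30 person-years, or 90 × 4 = 360 monthly visits if all are attended.
- On-ring events with no effect: 30 × 0.28 = 8.4.
- On-ring events with a 30% reduction: 8.4 × 0.70 = 5.88.
- Pre-ring events: 90 × 2/12 × 0.28 = 4.2.

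**4. Break-even**
- Gap to close: 8.4 − 5.88 = 2.52 events.
- As a share of on-ring visits: 2.52 / 360 = 0.7%.

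If the false-positive rate is 0.7 percentage points of visits higher on the ring than before it, the planned 30% reduction disappears. The percentage does not depend on the number of women: with 120, it is 3.36 / 480 = 0.7%.

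**5. What would produce 0.7%?** The documents do not say, so the following are assumptions. Let *q* be the share of on-ring visits with exactly two other signs and otherwise normal discharge, and *d* the chance that the ring makes discharge count as abnormal. Extra events = 360 × *q* × *d*. Observed ratio = (5.88 + extra) / 8.4, where the true ratio is 0.70.

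| *q* | *d* | Extra events | Observed ratio |
|---|---|---|---|
| 1% | 10% | 0.36 | 0.74 |
| 2% | 20% | 1.44 | 0.87 |
| 5% | 10% | 1.8 | 0.91 |
| 5% | 20% | 3.6 | 1.13 |
| 10% | 30% | 10.8 | 1.99 |

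**6. Allowing sign 4 before the ring as well.** Monthly risk is 1 − exp(−0.28/12) = 2.31% before and 1 − exp(−0.28 × 0.7/12) = 1.62% on the ring. Observed risk = true risk + (1 − true risk) × (two-sign share) × P(sign 4). Assume sign 4 is present at 10% of two-sign visits before the ring.

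| Two-sign share, P(sign 4) on ring | Ratio, share constant | Ratio, share also falls 30% on ring |
|---|---|---|
| 5%, 20% | 0.93 | 0.83 |
| 10%, 20% | 1.09 | 0.91 |
| 10%, 30% | 1.39 | 1.12 |

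Example for the first row: before, 0.0231 + 0.9769 × 0.05 × 0.10 = 0.0279; on the ring, 0.0162 + 0.9838 × 0.05 × 0.20 = 0.0260; ratio 0.93. With the share at 3.5% on the ring, the risk is 0.0162 + 0.9838 × 0.035 × 0.20 = 0.0231; ratio 0.83.

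**The case against.** **Nugent may already apply.** Sections 1.2, 5.1 and 7.2.1 can be read as making the Gram stain part of every BV diagnosis, and Section 4.1 pairs Amsel with Nugent for entry. A reader might infer that Amsel alone is the settled Aim 3 rule. The documents do not establish that. If confirmation was intended, discharge alone cannot create an event. This stands, but the sections that define the Aim 3 outcome do not say so.

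**The protocol does not say that the ring increases discharge.** A reader might infer this from Section 1.1. That sentence reports a pooled category, discharge or discomfort, for continuous use, against oral contraceptive users. This study's comparator is different: "women will be asked to maintain a one-month period of no hormonal contraceptive use" (Section 5.3), and participants may choose the non-continuous regimen (Section 5.4). Complaints are also not examination findings. This stands: the mechanism is plausible, not documented.

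**The confirmed outcome is already analyzed under Aim 1.** It is, as a secondary binary outcome, and a discrepancy with Aim 3 might reveal a discharge artefact. That analysis does not cover time to BV, and it leaves the primary definition exposed.

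**The modeled ratios rest on undocumented frequencies.** They do. Letting the two-sign share fall along with BV weakens the effect, some visits tipped by discharge may be true BV, and the 28 per 100 person-years carries no stated diagnostic definition, so it may already include such events. Only the break-even figure is free of assumed sign frequencies.

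**Odor overlap.** Malodor within sign 4 overlaps with the KOH odor sign, but the rule is the same in both periods, so it does not support a bias that depends on ring use.

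**Conclusion.** The concern holds in limited form. As written, Aim 3 has a primary outcome that can turn on an unblinded, visually judged sign that may be ring-related, with no stated confirmation. Any resulting bias would act against the hypothesized benefit.

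Its size cannot be derived from the documents. What can be derived is how little is needed: an excess false-positive rate of about 0.7% of on-ring visits, or about 2.5 events among 90 women, would cancel the planned 30% reduction. That figure rests on the plan's rate and effect size, a constant rate, one visit per ring month, and the plan's rate being free of such false positives.

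A reader might infer that the trial will hide or reverse a true reduction. The documents do not support that. The illustrative ratios run from 0.74 to 1.99, depending entirely on assumed frequencies.

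**What to change.** In Section 9.1, Aim 3:

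- Define the BV event, for both incidence and time to BV, as Amsel-positive and confirmed by Nugent score on that visit's Gram stain, as the Aim 1 secondary outcome already does.
- State how interim symptomatic visits without a Gram stain are counted. Tables 1 and 2 have no column for such visits.
- Add a sensitivity analysis that does not use discharge, with the same rule in both periods: either pH, clue cells and amine odor with a cut-off fixed in advance, or Nugent alone. Nugent alone is useful because, under the combined rule, discharge can still decide the Amsel part at a Nugent-positive visit.
- Report, by period, how many Amsel events depend on sign 4.

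Clinical diagnosis and treatment in Section 5.2.1 stay unchanged.

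**Cost.** Wording and a few lines of analysis; Section 6.3 already has Gram stain material collected at follow-up visits. The downside is fewer counted events in an outcome that already expects few, because Amsel-positive, Nugent-negative visits drop out, and possibly unstained interim visits too.
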